Clinical Trial Protocol

Document Number:		c30603221-08
EudraCT No.	2019-004932-40	
EU Trial No.	NA	
BI Trial No.	0135-0340	
BI Investigational Medicinal Product	alteplase (TPA-05, 50 mg/vial and TPA-02, 50 mg/vial)	
Title	Bioequivalence of alteplase derived from two different manufacturing processes following intravenous administration in healthy male volunteers	
Lay Title	A study in healthy men to compare 2 different formulations of alteplase	
Clinical Phase	I	
Clinical Trial Leader	
Phone: [REDACTED] Fax: [REDACTED]
	
Investigator	
Phone: [REDACTED] Fax: [REDACTED]
	
Status	Final Protocol (Revised Protocol (based on global amendment 7))	
Version and Date	Version: 8.0	Date: 14 April 2021
Page 1 of 98		

Proprietary confidential information © 2021 Boehringer Ingelheim International GmbH or one or more of its affiliated companies. All rights reserved. This document may not - in full or in part - be passed on, reproduced, published or otherwise used without prior written permission
		

CLINICAL TRIAL PROTOCOL SYNOPSIS

Company name	Boehringer Ingelheim
Protocol date	17 February 2020
Revision date	14 April 2021
BI trial number	0135-0340
Title of trial	Bioequivalence of alteplase derived from two different manufacturing processes following intravenous administration in healthy male volunteers
Investigator:	[REDACTED]
Trial site	[REDACTED]
Clinical phase	I
Trial rationale	To allow a change of manufacturing process of alteplase (new process: TPA-05)
Trial objective	To establish the bioequivalence of alteplase derived from two different manufacturing processes (new process, TPA-05, vs. current process, TPA-02)
Trial design	open-label, randomised, 2-way cross-over design with at least 24 h wash-out
Trial endpoints:	Primary endpoints: AUC_{0-tz} and C_{max} Secondary endpoints: $AUC_{0-\infty}$
Number of subjects	
total entered 72
 
each treatment 72
 
The trial part A was performed with 12 subjects and resulted in PK-data that cannot be used for the assessment of bioequivalence. Therefore part B of this trial will be performed following a 2-stage design with an adaptive sample size re-estimation. Initially 18 subject will be dosed (stage 1, Part B). After an interim analysis a maximum of 42 subjects may be dosed in stage 2 (Part B).

Diagnosis	Not applicable
Main criteria for inclusion	Healthy male subjects, age of 18 to 45 years (inclusive), body mass index (BMI) of 18.5 to 29.9 kg/m ² (inclusive)
Test product	alteplase, TPA-05 (50 mg vial)
dose	0.2 mg/kg body weight
mode of admin.	iv-infusion over 30 min

Proprietary confidential information © 2021 Boehringer Ingelheim International GmbH or one or more of its affiliated companies

Reference product	alteplase, TPA-02 (50 mg vial)
dose	0.2 mg/kg body weight
mode of admin.	iv-infusion over 30 min
Auxiliary medicinal product	Heparin-Natrium-5000-ratiopharm® (unfractionated heparin)
dose	5000 IU
mode of admin.	iv-bolus (5 min prior to start of each alteplase infusion)
Duration of treatment	single dose for each treatment
Statistical methods	
Part A:
 
Only descriptive analyses are performed since the generated PK-data that cannot be used for the confirmatory bioequivalence assessment.
 
Part B:
 
The study design is an adaptive two-stage group-sequential design allowing for unblinded sample size re-estimation after stage 1. The assessment of bioequivalence will be based upon 2-sided repeated confidence intervals (CIs) for the ratios of geometric means (test/reference) for the primary endpoints using an acceptance range of 80.00 to 125.00%. The alpha level for stage 1 is fixed to 0.03585 and a user-defined alpha spending function will be used such that the full level of 0.05 is spent at the final analysis. The final analysis will be performed according to the inverse normal approach.
 
The statistical model for each stage of the trial will be an analysis of variance (ANOVA) on the logarithmic scale including effects for sequence, subjects nested within sequences, period and treatment. p-values will be calculated based on the residual error from the ANOVA and the t-distribution.
 
Descriptive statistics will be calculated for all endpoints.

Proprietary confidential information © 2021 Boehringer Ingelheim International GmbH or one or more of its affiliated companies

FLOW CHART

Trial period	Visit	Day	Planned time (relative to start of infusion [h:min])	Approximate clock time of actual day [h:min]	Event and comment	Safety laboratory	Alteplase Infusion	PK blood (x) / ADA (y)	Biomarkers ⁸	Vital signs (BP, PR)	Questioning for AEs and concomitant therapy ⁶
SCR	1	-21 to -1			Screening (SCR) ¹	A				x	
	2	-1	-12:00	20:00	Admission to site, check of restrictions	x ⁵				x	
		1	-1:30	06:30	Allocation to treatment ²			x ²	x ^{2,8}	x ²	x ²
			-0:15	07:45		B		x,y	x ^{8,9}		
			-0:05	07:55	i.v.-bolus of standard heparin						
			0:00	08:00	Start of alteplase infusion		▲				
			0:05	08:05				x			
			0:10	08:10				x			
			0:15	08:15				x			
			0:20	08:20				x			
			0:25	08:25				x	x ⁸		
			0:30	08:30	End of infusion		▼	x			x
			0:32	08:32				x			
			0:34	08:34				x			
			0:36	08:36				x			
			0:40	08:40				x			
			0:45	08:45				x			
			0:50	08:50				x			
			1:00	09:00	240 mL fluid intake			x	x ^{8,9}		x
			1:20	09:20				x			
			1:40	09:40				x			
			2:00	10:00	Snack , 240 mL fluid intake			x	x ⁸		x
			3:00	11:00	Assessment of local tolerability			x			x
			4:00	12:00	lunch ³	B		x		x	x
			6:00	14:00				x			x
			7:30	15:30	Snack						
			10:45	18:45	Assessment of local tolerability ¹⁰ (all subjects together)	x ⁷					x ¹⁰
			11:00	19:00	Dinner						
	3	1	-1:30	06:30				x ²	x ^{2,8}	x ²	x ²
			-0:15	07:45		B		x	x ^{8,9}		
			-0:05	07:55	i.v.-bolus of standard heparin						
			0:00	08:00	Start of alteplase infusion		▲				
			0:05	08:05				x			
			0:10	08:10				x			
			0:15	08:15				x			
			0:20	08:20				x			
			0:25	08:25				x	x ⁸		
			0:30	08:30	End of infusion		▼	x			x
			0:32	08:32				x			
			0:34	08:34				x			
			0:36	08:36				x			
			0:40	08:40				x			
			0:45	08:45				x			
			0:50	08:50				x			

Treatments periods will be performed on 2 consecutive days

Proprietary confidential information © 2021 Boehringer Ingelheim International GmbH or one or more of its affiliated companies

			1:00	09:00	240 mL fluid intake			x	x ^{8,9}		x
			1:20	09:20				x			

Period	Visit	Day	Planned time (relative to start of infusion [h:min])	Approximate clock time of actual day [h:min]	Event and comment	Safety laboratory	Alteplase Infusion	PK _{blood} (x) / ADA (y)	Biomarkers ⁸	Vital signs (BP, PR)	Questioning for AEs and concomitant therapy ⁶
3	1	1	1:40	09:40				x			
			2:00	10:00	Snack, 240 mL fluid intake			x	x ⁸		x
			3:00	11:00	Assessment of local tolerability			x			x
			4:00	12:00	lunch ³	B		x		x	x
			6:00	14:00				x			x
			7:30	15:30	Snack						
			10:45	18:45	Assessment of local tolerability ¹⁰ (all subjects at that time)						x ¹⁰
			11:00	19:00	Dinner						
		2	24:00	08:00	Assessment of local tolerability, Breakfast (voluntary), discharge from trial site	B		x ⁸	x	x	
EOT	4		8-22		End of trial (EOT) examination ⁴	C			x	x	

1. Subject must be informed and written informed consent obtained prior to starting any screening procedures. Screening procedures include physical examination, check of vital signs, ECG, safety laboratory (including drug screening, fecal occult blood test), demographics (including determination of body height and weight, smoking status and alcohol history), relevant medical history, concomitant therapy and review of inclusion/exclusion criteria. Pharmacogenetic samples will be collected if needed.
2. The time is approximate; the procedure is to be performed and completed within 3 h prior to drug administration.
3. If several actions are indicated at the same time point, the intake of meals will be the last action.
4. End of trial examination includes physical examination, vital signs, ECG, safety laboratory, recording of AEs and concomitant therapies.
5. Only urine drug screening and alcohol breath test
6. AEs and concomitant therapies will be recorded throughout the trial, but will be specifically asked for at the time points indicated in the Flow Chart above.
7. Urine stix only

10. tolerance time for these measurements is ± 90 min

TABLE OF CONTENTS

TITLE PAGE	1
CLINICAL TRIAL PROTOCOL SYNOPSIS	2
FLOW CHART	4
TABLE OF CONTENTS	6
ABBREVIATIONS	11
1. INTRODUCTION.....	14
1.1 MEDICAL BACKGROUND.....	14
1.2 DRUG PROFILE OF ALTEPLASE.....	15
1.2.1 General information	15
1.2.2 Paradox effect of alteplase on the coagulation system.....	15
1.2.3 Safety in patients after systemic administration of Actilyse®	17
1.2.4 Clinical experience with alteplase in healthy subjects.....	17
1.2.6 Residual Effect Period	28
1.3 DRUG PROFILE OF HEPARIN	28
1.4 RATIONALE FOR PERFORMING THE TRIAL	28
1.4.2 Rationale for bioequivalence trial in humans	29
1.5 BENEFIT - RISK ASSESSMENT	29
1.5.1 Procedure-related risks	30
1.5.2 Risk resulting from the trial design.....	30
1.5.3 Drug-related risks and safety measures.....	30
1.5.3.1 Risks associated to alteplase administration	30
1.5.3.2 Risk associated to heparin administration.....	33
1.5.3.3 Risk of combined administration of alteplase and heparin.....	34
1.5.3.4 Drug-induced liver injury (DILI).....	34
1.5.4 Overall assessment	35
2 TRIAL OBJECTIVES AND ENDPOINTS.....	36
2.1 MAIN OBJECTIVES, PRIMARY AND SECONDARY ENDPOINTS	36
2.1.1 Main objectives.....	36

Proprietary confidential information © 2021 Boehringer Ingelheim International GmbH or one or more of its affiliated companies

2.1.2 Primary endpoints	36

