To mitigate the bleeding risk the following safety measures have been undertaken:

- A low dose of 0.2 mg/kg has been chosen
- A minimum body weight of 65 kg has been defined (see [3.3.2](#))
- Trial specific exclusion criteria have been defined to exclude subjects who are perceived to have an increased risk of bleeding (see [3.3.3](#))
- Trial specific restrictions have been defined to reduce the risk of injury prior to dosing (see [4.2.2](#))
- Inhouse confinement of 24 h after start of infusion (covering the complete elimination of alteplase and heparin) to reduce the risk of injury after dosing
- Thorough lab testing (including urinestix)
- Frequent AE-questioning (focus on bleeding events)

Considering the mode of action of alteplase focusing on fibrin bound plasminogen, taking into account the safety measures described above and referring to the good tolerability of rt-PA infusions in the cited healthy volunteer trials the bleeding risk for healthy subjects participating in this trial is expected to be low.

Subcutaneous hematomas at the injection site of i.v.-catheters are typical procedure related side effect in clinical trials. They happen more often with anticoagulants and are expected also in this trial. Subcutaneous hematomas are no undue risk to healthy subjects. At the time points given in the [Flow Chart](#) inspections of the injection sites will be performed. If necessary cooling bags may be applied.

Risk of thromboembolic complications

In part A of the trial clinical observations have been made indicating a procoagulant status. An increase of fibrin/fibrinogen degradation products has been reported also in previous trials in healthy subjects [[P86-5232](#), [P87-3595](#)]. However, at that time the origin of the fibrin in healthy subjects was unclear.

Meanwhile it is known that fibrinolytic therapy is associated with a paradox thrombin stimulation. An increased generation of F1+2 (marker of thrombin generation), TAT (marker of thrombin activity) and FPA (marker of thrombin activity) after start of alteplase infusion has been demonstrated in several clinical trials (for references see [1.2.2](#)).

Proprietary confidential information © 2021 Boehringer Ingelheim International GmbH or one or more of its affiliated companies

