5.2.5 Other safety parameters

5.2.5.1 Local tolerability

Local tolerability will be assessed by the investigator on the basis of swelling, induration, heat, redness, pain, and other findings. Abnormal findings will be recorded as adverse event.

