7.3.4 Safety analyses

Safety will be analysed based on the assessments described in Section [2.2.2.2](#). All treated subjects (TS, refer to Section [7.2](#)) will be included in the safety analysis. Safety analyses will be descriptive in nature and based on BI standards. No hypothesis testing is planned.

For all analyses, the treatment actually administered (= treatment at onset) to the subject will be used (any deviations from the randomised treatment will be discussed in the minutes of the Report Planning Meeting).

Treatments will be compared in a descriptive way. Tabulations of frequencies/proportions will be used to evaluate categorical (qualitative) data, and tabulations of descriptive statistics will be used to analyse continuous (quantitative) data.

Measurements (such as ECG, vital signs, or laboratory parameters) or AEs will be assigned to treatments (see Section [4.1](#)) based on the actual treatment at the planned time of the measurement or on the recorded time of AE onset (concept of treatment emergent AEs).

Therefore, measurements planned or AEs recorded prior to first intake of trial medication will be assigned to the screening period, those between first trial medication intake and end of REP (see Section [1.2.3](#)) will be assigned to the treatment period. Events occurring after the REP but prior to next intake or end of trial termination date will be assigned to 'follow-up'. In case of two or more treatments, the follow-up will be summarized according to the previous treatment. These assignments including the corresponding time intervals will be defined in detail in the Trial statistical analysis plan (TSAP). Note that AEs occurring after the last per protocol contact but entered before final database lock will be reported to Pharmacovigilance only and will not be captured in the trial database.

Additionally, further treatment intervals (analysing treatments) may be defined in the TSAP in order to provide summary statistics for time intervals, such as combined treatments, on-treatment totals, or periods without treatment effects (such as screening and follow-up intervals).

Adverse events will be coded using the Medical Dictionary for Regulatory Activities (MedDRA). Frequency, severity, and causal relationship of AEs will be tabulated by treatment, system organ class, and preferred term. SAEs, AESIs (see Section [5.2.6.1](#)), and other significant AEs (according to ICH E3) will be listed separately.

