6. GENERAL ANALYSIS DEFINITIONS

6.1 TREATMENTS

For basic study information on treatments to be administered, assignment of treatment groups, and selection of doses, cf. Section 4 of the CTP.

All subjects will receive the 2 treatments (TPA-02 and TPA-05) in randomised order at 2 consecutive days. The specific alteplase dose to be administered to a given subject will be calculated based on the body weight measured at screening examination. Prior to the first administration of trial medication, subjects will be assigned to treatment sequences T-R or R-T.

For statistical analysis of AEs, safety laboratory data, vital signs and ECG, the following analysis phases are defined for each subject:

Table 6.1: 1 Flow chart of analysis phases for statistical analyses of AEs, safety laboratory and vital signs

Study analysis phase	Label	Start (inclusive)	End (exclusive)
Screening	Screening	Date of informed consent	Date/time of first administration of TPA-02/ TPA-05
On-treatment	TPA-02 0.2 mg/kg body weight	Date/time of first administration of TPA-02	Date/time of first administration of TPA-05 or 12:00 a.m. on day after subject's trial termination date, whichever occurs earlier
On-treatment	TPA-05 0.2 mg/kg body weight	Date/time of first administration of TPA-05	Date/time of first administration of TPA-02 or 12:00 a.m. on day after subject's trial termination date, whichever occurs earlier

Analysis phases for statistical analysis of AEs are defined for each subject as described in the table above.

CTR Section 15, Appendix 16.1.13.1.8.2 and Appendix 16.1.13.1.8.3 AE displays will present results for the on-treatment phase and screening phase.

In CTR Section 15 AE tables (but not in Appendix 16.1.13.1.8.2 and Appendix 16.1.13.1.8.3 AE tables), the following totals will be provided in addition:

- **"Total on-trt"**, defined as the total over all on-treatment phases involving BI

Safety laboratory data and vital signs will be analysed by treatment (TPA-02 or TPA-05).

More details on the technical implementation of these analyses are provided in the ADS Plan of this TSAP.

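### Local-tolerability inspections differ between periods: none is scheduled between 10:45 after the first infusion and 3:00 after the second, and the 24 h check follows only the second infusion

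*Protocol*

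**What the plan says.** In the protocol's Flow Chart, Visit 2 (first infusion) has "Assessment of local tolerability" at 3:00 and again at 10:45, the latter marked "all subjects together" and carrying a ±90 min tolerance in footnote 10. Visit 3 (second infusion) has the same two checks and a third at 24:00 on Day 2: "Assessment of local tolerability, Breakfast (voluntary), discharge from trial site". The Visit 3 pre-dose rows at -1:30 and -0:15 list no local-tolerability check. The -1:30 row does list vital signs and adverse-event questioning.

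Protocol section 1.5.3.1 expects subcutaneous hematomas at catheter sites and says that at the Flow Chart times "inspections of the injection sites will be performed". Section 5.2.5.1 makes local tolerability an investigator assessment of swelling, induration, heat, redness, pain and other findings, and adds: "Abnormal findings will be recorded as adverse event".

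Protocol section 7.3.4 assigns adverse events by recorded onset and says: "Treatments will be compared in a descriptive way". In SAP Table 6.1: 1 the TPA-02 phase ends at "Date/time of first administration of TPA-05 or 12:00 a.m. on day after subject's trial termination date, whichever occurs earlier". The TPA-05 row mirrors it.

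**The concern.** The Flow Chart is the control that section 1.5.3.1 relies on for an expected local reaction, and it is not the same for the two infusions. After the first infusion, scheduled inspection stops at 10:45 and resumes only when the second product has been on board for 3 h. The documents give no reason for the difference.

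Two things are at stake. First, no investigator inspection of the sites is scheduled before the second heparin and alteplase dose. Second, ascertainment of late site findings depends on period, and a finding first seen at Visit 3 3:00 has to be dated back across the second infusion to be tabulated under the product that preceded it. The documents do not say how to date the onset of a finding first seen at an inspection. Nor do they say how to record which infusion's cannula site it concerns.

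**Working it through.** No planned figure in the documents bears on this point, so there is none to reproduce. The check is clock arithmetic on the Flow Chart, followed by a short dilution formula.

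**Inputs**
- Inspection times: Flow Chart, Visits 2 and 3.
- Tolerance of ±90 min on the 10:45 check: Flow Chart footnote 10.
- Infusion starts at least 24 h apart, on consecutive days: protocol section 6.2.2 and the Flow Chart. The calculation uses exactly 24 h; a longer interval lengthens the gap.
- Pre-dose procedures completed within 3 h before dosing: Flow Chart footnote 2.
- Sequences randomised 1:1: protocol section 7.6.
- Part B size of 18 subjects in stage 1 and at most 42 in stage 2: protocol section 3.3.

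**Schedule**

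| Check | After infusion 1 | After infusion 2 |
|---|---|---|
| 3:00 | yes | yes |
| 10:45 | yes | yes |
| About 24 h | none | 24:00 |

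**Gap across the second dose**
- Gap = 24:00 + 3:00 - 10:45 = 16:15 (18:45 to 11:00 the next day on the Flow Chart clock).
- With the tolerance: 16:15 - 1:30 = 14:45, and 16:15 + 1:30 = 17:45.
- Before the second infusion starts: 24:00 - 10:45 = 13:15. After it starts: 3:00.

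**What falls inside the gap**
- Questioning at Visit 3 -1:30 comes 24:00 - 1:30 = 22:30 after the start of the first infusion, and 22:30 - 10:45 = 11:45 after the last inspection.

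**Who gets an inspection at about 24 h**
- Each product has one only in subjects who receive it second: 18/2 = 9 of 18 in stage 1, and (18 + 42)/2 = 30 of 60 at the Part B maximum, assuming complete and balanced sequences.

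**Effect on the tabulated comparison**

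Let rT and rR be the rates of late site findings (after 10:45) caused by test and reference. Let f be the fraction of late period 1 findings whose onset is recorded as a detection time after the second infusion. Assume 1:1 sequences, all late findings detected, and no subject with late findings from both infusions.
- Tabulated T = 0.5·rT + 0.5·(1 - f)·rT + 0.5·f·rR
- Tabulated R = 0.5·rR + 0.5·(1 - f)·rR + 0.5·f·rT
- Difference = (1 - f)·(rT - rR)

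The documents give neither the rates nor f. With assumed rates of 20% and 10%:

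| f | Tabulated T | Tabulated R | Difference |
|---|---|---|---|
| 0 | 20% | 10% | 10 points |
| 0.5 | 17.5% | 12.5% | 5 points |
| 1 | 15% | 15% | 0 points |

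Only findings after 10:45 that began before the second infusion are exposed to this. Earlier findings are unaffected.

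**The case against.** The strongest reply is that assignment follows onset and not detection. Section 5.2.6.2.1 requires a time of onset in every adverse-event record, and an onset before the second infusion stays with the first product under SAP Table 6.1: 1. A reader might infer that late first-product findings are automatically counted under the wrong product, or that the comparison is driven to no difference. The documents do not support that. The zero-difference row above is the extreme case in which every late period 1 finding is dated at detection. This part of the objection stands.

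A reader might also infer that less than half of the first 24 h is covered (10.75/24 = 45%). Inspections are point checks. A finding that arises after 10:45 and persists can still be seen at Visit 3 3:00 and dated back, so the gap between inspections is the fair measure.

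Subjects are in-house and under observation between the two infusions, staff assess them as needed, and section 1.5.3.1 promises frequent questioning focused on bleeding. This narrows the gap but does not close it. Section 5.2.6.2.1 describes the routine questioning as non-specific, and neither it nor general observation is the investigator assessment defined in section 5.2.5.1.

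The 24:00 check coincides with discharge, which may explain the asymmetry. Section 1.5.3.1 also calls these hematomas no undue risk, and it promises inspections only at Flow Chart times, so the documents do not contradict themselves. All of this stands and limits the weight of the point. Safety analyses are descriptive, local findings enter as ordinary adverse events, and with 1:1 sequences the extra period 2 check favours neither product.

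**Conclusion.** The point holds as a difference in ascertainment between periods. There are two scheduled inspections after the first infusion and three after the second, with a 16 h 15 min gap (14 h 45 min to 17 h 45 min) spanning the second dose. These figures come directly from the Flow Chart, given infusion starts 24 h apart.

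Misattribution is a conditional risk. For a finding that began before the second infusion, it requires onset to be recorded as the later detection time, and the difference then shrinks by the factor (1 - f), with f unknown. A finding that truly begins after the second infusion is assigned to the second product by the plan's own rule, and the schedule does not alter that.

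The consequences are possible under-detection of late period 1 findings and possible dilution of a descriptive comparison. There is no systematic shift towards either product and no effect on the bioequivalence test. The change is worth making because it costs little and gives both products similar ascertainment.

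**What to change.** Add "Assessment of local tolerability" to the Visit 3 -1:30 row of the Flow Chart, beside the vital signs and adverse-event questioning already there. The check then falls nominally 22:30 after the start of the first infusion, and no earlier than 24:00 - 3:00 = 21:00 under footnote 2. Both infusions would have inspections at 3:00, 10:45 and about 24 h. Findings at the added check would fall in the first product's phase under SAP Table 6.1: 1 without changing that table. The longest interval between inspections across the second dose would drop from 16:15 to 11:45 (10:45 to 22:30), at nominal times.

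Add one sentence to the protocol or SAP: for site findings first seen after the second infusion, record whether the site is a period 1 or period 2 cannula site, record the best-estimated onset, and keep assignment by onset. Later findings at period 1 sites should not all be assigned automatically to the first product. That would override the onset rule, and section 1.5.3.1 attributes earlier bleeding events partly to alteplase acting on injuries already present, so a second dose may cause bleeding at an older site.

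The cost is one Flow Chart entry, one sentence and one brief visual check per subject at a time when staff are already with the subject. No extra visit or sample is needed.
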